Protocol

A) CLINICAL TRIAL IDENTIFICATION

Title	Use of Music Therapy as an Intervention to Reduce Anxiety in Patients With Localized Breast Cancer		
Short title	CENSORIAL		
Coordonnateur	[name] Study nurse ICO Site Angers [contact]		
Estimated number of centers	1	Number of subjects	27
Inclusion period	18 months	Overall duration	24 months
Subject participation duration	5 months		

B) SPONSOR IDENTIFICATION

Sponsor name	ICO, DRC-Cellule de Promotion
Contact	[name] [name] [contact]

C) SYNOPSIS

Breast cancer is the most common cancer among women worldwide, with 58,500 new cases reported in metropolitan France in 2018. The diagnosis of cancer, the explanation of treatment modalities, and their potential adverse effects can generate distressing emotions, such as fear, and the resources available to cope with these emotions vary among patients. Attending the hospital for outpatient chemotherapy administration is, in itself, a potential source of anxiety.

The use of music as part of a therapeutic approach constitutes an intervention that may help patients reduce the intensity of distressing emotions. "Active" music therapy involves the patient's participation through the use of instruments, vocal expression, or rhythmic body movement, without requiring any prior musical skills. The presence of a certified music therapy professional is essential, particularly to support and manage the emotions that may arise during sessions. These sessions may be conducted individually or in groups. In the context of breast cancer, music therapy has demonstrated benefits in reducing pain, anxiety, depressive symptoms, and length of hospital stay in patients undergoing mastectomy.

⇒ **This controlled, randomized study aims to assess the effect of music therapy on reducing anxiety in patients with localized breast cancer receiving outpatient chemotherapy, compared with a control group without musical intervention.**

D) INFORMATION

Design	The study has the following characteristics: 
 • Single-center study • Controlled study • Randomized study (2:1 allocation ratio) • Open-label study • Prospective study • Parallel-group design
Primary objective	To evaluate the effect of music therapy on anxiety levels in patients with breast cancer receiving adjuvant or neoadjuvant chemotherapy.
Primary endpoint	Anxiety will be assessed using the STAI scale (Trait form YB and State form YA). The STAI State score will be collected before and after chemotherapy administration during the first three chemotherapy sessions in both the music therapy and control

	groups. The mean pre- and post-chemotherapy difference in STAI State scores will be compared between the music therapy and non-music therapy groups.
Secondary objectives and endpoints	
Secondary objectives are to evaluate the effect of music therapy by comparing the two groups (with and without music therapy) on:
 
 a. Changes in anxiety levels between the first and the third chemotherapy sessions, measured using the STAI State score (before the first session and before the third session). b. Changes in anxiety levels between the first and the last chemotherapy sessions, measured using the STAI State score (before the first session and before the last session). c. Changes in quality of life, measured using the PROMIS-29 questionnaire at study inclusion, at the end of the third chemotherapy session, and at the end of all chemotherapy sessions. d. The presence of anticipatory nausea (i.e., nausea occurring before chemotherapy administration) assessed before the first three chemotherapy sessions and before the last chemotherapy session, using a 0–10 numeric rating scale.
Inclusion criteria	
 1. Female patient with localized breast cancer 2. Indication for adjuvant or neoadjuvant chemotherapy 3. Age ≥ 18 years 4. Signed informed consent 5. Patient covered by a national health insurance system
Exclusion criteria	
 1. Metastatic breast cancer 2. Triple-negative breast cancer (HR–: ER–, PR– and HER2–) 3. Patient not eligible for curative surgery 4. Prior treatment with chemotherapy 5. Uncorrected hearing loss 6. Pregnant or potentially pregnant woman, or breastfeeding 7. Presence of a major depressive episode or psychotic disorder at the time of the diagnostic consultation 8. Patient unable to understand French 9. Cognitive impairment or inability to understand study requirements 10. Vulnerable patient under legal protection (safeguard of justice, guardianship, or curatorship)

E) DESCRIPTION OF STUDY INTERVENTIONS

Description of the Music Therapy Intervention

In the experimental group, a music therapy session conducted by a certified music therapist will be offered to the patients. The session will take place before the administration of chemotherapy during the 1st, 2nd, and 3rd treatment cycles. Each session will last 1 hour.

The activity program will be defined during the first individual session. The sessions will follow three progressive processes:

Activities	Patient Involvement
Instrumental music (violin, guitar, singing) Relaxation suggestions (e.g., imagery associated with the music resonating in the body) Suggestion of music listening at home Invitation to instrumental improvisation Vocal warm-up	Active listening Attention to bodily sensations
Instrumental music as an introduction Invitation to instrumental improvisation	Selection of music pieces

Vocal warm-up Suggestion to use music as a relaxation tool at home	Physical involvement in playing a musical instrument (hang, senzula, percussion instruments)
Musical introduction based on the patient's choice Vocal warm-up Singing an existing song or engaging in songwriting (brainstorming, selecting a melody, singing the composition with the music therapist) Discussion on the use of music to improve mood and reduce feelings of fatigue	Active listening or instrumental play Songwriting Verbalization of emotional experiences

Description of Quality-of-Life Questionnaires:

Participants will be asked to complete the following quality of life questionnaires (see the assessment schedule for the timing of questionnaire administration):

STAI (State/Trait):

The State Trait Anxiety Inventory (STAI), developed by Spielberger et al. (1983), is a self assessment questionnaire. The French version was validated by Bruchon Schweitzer et al. in 1993 (Manuel de l'inventaire d'anxiété état trait – forme Y).

This scale includes two components:

- State Anxiety, which reflects the patient's current emotional state and allows assessment of nervousness and worry during the session.
- Trait Anxiety, which reflects the patient's general and habitual emotional state.

PROMIS 29:

The PROMIS 29 Profile v2.0 assesses pain intensity using a single numeric rating item (0 to 10) and evaluates seven health domains (physical function, fatigue, pain interference, depressive symptoms, anxiety, ability to participate in social roles and activities, and sleep disturbance), using four items per domain.

STUDY ASSESSMENT SCHEDULE

VISITS	INCLUSION PERIOD	TREATMENT PERIOD						FOLLOW UP PERIOD	
Dates des visites		Cycle 1		Cycle 2		Cycle 3		Last cycle	M6 end of treatment
Delay		Before start of musicotherapy	End of chemotherapy	Before start of musicotherapy	End of chemotherapy	Before start of musicotherapy	End of chemotherapy		
Inclusion / Exclusion criteria	X								
Informed consent	X								
Randomisation (2:1)	X								
PRO (Patient Reported Outcome)									
STAI YB (trait)		X							X
STAI YA (état)		X	X	X	X	X	X		
QLQ C30		X					X	X	
BR23		X					X	X	
Numerical scale 0-10 (nausea)		X					X	X	
INTERVENTION									
Arm 1 : musicotherapy		Before chemotherapy		Before chemotherapy		Before chemotherapy			
Arm 2 : control

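### Secondary endpoint a measures anxiety after two of the three music sessions, and as scheduled no pre-chemotherapy State score follows the third

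*Protocol*

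**What the plan says.** Section D of the Protocol lists two secondary endpoints that follow STAI State anxiety from one chemotherapy session to a later one. Endpoint a is "measured using the STAI State score (before the first session and before the third session"). Endpoint b is "measured using the STAI State score (before the first session and before the last session").

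Section E gives the timing of the intervention: "The session will take place before the administration of chemotherapy during the 1st, 2nd, and 3rd treatment cycles". It introduces the content with "The sessions will follow three progressive processes", followed by a table with three rows of activities.

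The Study Assessment Schedule splits each of Cycles 1 to 3 into two columns. The first is headed "Before start of musicotherapy" and the second is the time after chemotherapy. STAI YA (State) is marked in all six of these columns. It has no mark under the last cycle or at the M6 visit.

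**The concern.** The secondary objectives are framed as the effect of music therapy, and the programme has three sessions. A reader who sees a result for endpoint a will tend to take it as the result for the programme. If the State score ahead of session 3 is taken before that day's music hour, the third session cannot have contributed to it.

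This would matter little if a later pre-session score filled the gap. Endpoint b is meant to do so, but it depends on a form that the schedule does not ask for. Without that form, a null result on endpoint a could not be read as showing that three sessions leave anxiety ahead of chemotherapy unchanged. A positive result would likewise say nothing about the third session.

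**Working it through.** The Protocol gives no figure to reproduce here. The check is a count of music sessions completed at each anxiety measurement in the music arm.

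**Inputs**
- Music sessions: one before chemotherapy in each of Cycles 1, 2 and 3, so three in total (section E).
- Pre-score in Cycles 1 to 3: before the music starts (schedule column heading).
- Post-score in Cycles 1 to 3: after chemotherapy, hence after that day's music (schedule).
- Endpoint time points: section D, items a to c.

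**Count.** For Cycle k = 1, 2, 3, the sessions completed at the pre-score are k − 1 and at the post-score k. From Cycle 4 on, the count stays at 3.

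| Measurement | Music sessions completed | State score ahead of chemotherapy? | Marked in the schedule? |
|---|---|---|---|
| State, before Cycle 1 | 0 | yes | yes |
| State, after Cycle 1 | 1 | no | yes |
| State, before Cycle 2 | 1 | yes | yes |
| State, after Cycle 2 | 2 | no | yes |
| State, before Cycle 3 (end of endpoint a) | 3 − 1 = 2 | yes | yes |
| State, after Cycle 3 | 3 | no | yes |
| State, before last cycle (end of endpoint b) | 3 if there are more than three cycles; 2 if Cycle 3 is the last | yes | **no** |
| PROMIS-29, end of third chemotherapy session (endpoint c) | 3 | no | no; QLQ C30 and BR23 are listed instead |
| STAI Trait, M6 | 3 | no | yes |

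**Reading the table**
1. Endpoint a ends at a count of 2.
2. A measurement meets the need only if it has a count of 3, is a State score ahead of chemotherapy, and is scheduled. No row meets all three conditions. The row for endpoint b meets the first two when chemotherapy runs beyond Cycle 3, and fails the third.
3. The blank is specific to the State row. The QLQ C30, BR23 and nausea rows all carry a mark under the last cycle, so that column is in use.

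**Could the text of endpoint a mean a score taken between the music hour and chemotherapy?** On the wording of section D alone it could. The schedule, however, provides only one score ahead of chemotherapy per cycle, and it is before the music. Moving both scores to after the music would also put the Cycle 1 baseline after the first session, which would not repair the endpoint.

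**The case against.** The best case for the plan has several parts.

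- **Endpoint a does what it says.** It names both time points, and both arms are measured at the same cycles. A reader might infer that it is biased toward no effect. It is not: for the effect after two sessions, which is what it defines, the Protocol gives no ground for claiming bias. A score taken before the day's music is also a defensible choice, because it keeps anticipatory anxiety apart from the immediate effect of that hour. This stands.

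- **Other anxiety measures do follow all three sessions.** A reader might infer that the trial has no anxiety measure after the full programme. That is too strong. The State score after chemotherapy in Cycle 3 follows the third session and enters the primary endpoint ("The STAI State score will be collected before and after chemotherapy administration during the first three chemotherapy sessions"). Endpoint c is "measured using the PROMIS-29 questionnaire at study inclusion, at the end of the third chemotherapy session, and at the end of all chemotherapy sessions", and that instrument "evaluates seven health domains (physical function, fatigue, pain interference, depressive symptoms, anxiety" among others. STAI Trait is marked at M6. None of these replaces a pre-session State score. The Cycle 3 post-score is a same-day, post-chemotherapy state, and no endpoint sets it against the Cycle 1 pre-score. PROMIS-29 at the end of session 3 has the same timing and no row in the schedule. The Trait form measures the patient's usual level of anxiety, not the current one.

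- **Endpoint b already covers the need in the text.** This stands in part. The intention is in section D, but the schedule does not collect the form. It would be tempting to add that the last session falls at a different distance from the programme in each patient. The Protocol gives neither the number of cycles nor the regimens, so that would be an assumption.

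- **The rows of activities are not numbered by session.** A reader might infer that the singing or songwriting row always comes after endpoint a is measured. Taking the rows in order as sessions 1 to 3 is the natural reading, but the Protocol does not say so. The count in the table does not need it.

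**Conclusion.** The point holds in a limited form. Endpoint a reflects two of the three music sessions, and as scheduled no State score ahead of chemotherapy follows the third. Endpoint b's text calls for such a score, and the schedule does not provide it.

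This limits what two secondary endpoints can show. It is not an internal contradiction in endpoint a, and it does not touch the primary endpoint. The share of the full-programme effect that endpoint a captures cannot be stated. A reader might turn two of three sessions into two thirds of the effect, but that needs benefit to accumulate evenly, and nothing in the Protocol supports this. If benefit levels off after the first session, nothing is lost; if it comes mostly from the third, most of it is missed.

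Two assumptions remain: that the schedule's marks are read correctly from the table, and that at least some patients have more than three cycles. Where Cycle 3 is the last cycle, endpoint b has the same time points as endpoint a and no later pre-session score can exist.

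**What to change.** 1. Keep endpoint a as defined, and label it as the change in pre-session State anxiety after two music sessions.
2. Add one STAI YA completion in both arms before the first chemotherapy after Cycle 3, for patients with a further cycle planned. Analyse the change from before session 1 to that point as an additional secondary endpoint.
3. Add the STAI YA mark before the last cycle in the schedule, so that endpoint b can be computed.

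**Cost.** One or two more self-completed forms per patient, at visits the patient attends anyway, and one more column in the schedule. With 27 subjects that is at most 2 × 27 = 54 forms, and fewer where the fourth cycle is also the last, since one form then serves both purposes. The drawback is that patients with only three cycles contribute no value at the new time point, so their number should be reported by arm.

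### Endpoints b and d end at an undefined last session with no assessment between it and Cycle 3, so an unannounced stop at session 4 or later loses the final score

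*Protocol*

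**What the plan says.** Protocol, D) Information, secondary objectives and endpoints:

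- Endpoint b is the change in STAI State between the first and the last chemotherapy session, "measured using the STAI State score (before the first session and before the last session".
- Endpoint d is anticipatory nausea, "assessed before the first three chemotherapy sessions and before the last chemotherapy session, using a 0–10 numeric rating scale".
- Endpoint a, by contrast, is tied to numbered sessions: "before the first session and before the third session".

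Section E) confines the music programme to the early cycles: "The session will take place before the administration of chemotherapy during the 1st, 2nd, and 3rd treatment cycles". The eligibility criterion is "Indication for adjuvant or neoadjuvant chemotherapy". The protocol states no regimen, number of cycles or cycle interval.

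The study assessment schedule gives Cycles 1, 2 and 3 a before and an end column each. A single Last cycle column follows, not split into before and after, and then the M6 column. No visit lies between Cycle 3 and Last cycle. The STAI State row has six marks, all within Cycles 1 to 3. The nausea row has three: before Cycle 1, at the end of Cycle 3, and at Last cycle.

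**The concern.** A score before the last session can be taken only if staff know beforehand that the session will be the last. For a patient who completes her plan, they know. For a patient whose treatment ends unexpectedly after Cycle 3, they learn it only once the session has passed. State anxiety describes how the patient feels at that moment, so it cannot be filled in later, and no analysis plan can restore a score that was never collected.

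Endpoint b is the only State comparison that reaches beyond the music programme, so it carries the question of whether any benefit lasts. The likely reasons for stopping early (toxicity, nausea, distress) lie close to what b and d measure. If those patients drop out of b and d, both endpoints are estimated mainly in women who tolerated their chemotherapy.

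**Working it through.** The point is about which scores are collected, so the main check sets the endpoint text against the schedule. The arithmetic only gives scale.

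**1. Required and scheduled scores**

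- State before session 1: required by a and b; marked.
- State before session 3: required by a; marked.
- State before the last session: required by b; no mark under Last cycle for any patient.
- Nausea before session 1: required by d; marked.
- Nausea before sessions 2 and 3: required by d; not marked (the Cycle 3 mark is at the end of chemotherapy).
- Nausea before the last session: required by d; marked under Last cycle, without saying that it precedes chemotherapy.

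**2. Which early stops lose the final score**, reading last as the session actually received last and following the endpoint text:

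- Stop at session 2 or 3: the endpoint text calls for nausea before each of these sessions, and State is scheduled before each. The final score exists.
- Stop decided before the session takes place: the score can be taken. It exists.
- Stop without notice at session 4 or later, before the planned end: no assessment was due at that session. The score does not exist, and the latest State score is the one at the end of Cycle 3.

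If last means the planned last session, a patient who stops early never reaches that time point. The protocol does not say which reading applies.

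**3. How many patients**

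- Inputs from section A): "Number of subjects 27". From section D): 2:1 allocation. If all 27 are randomised exactly 2:1, there are 27 × 2/3 = 18 music and 27 × 1/3 = 9 control patients.
- Share of an arm per lost patient: 1/9 = 11.1% of controls; 1/18 = 5.6% of the music arm.
- The protocol gives no stopping rate. Assuming 5%, 10% and 20% stop unexpectedly: 27 × 0.05 = 1.35, 27 × 0.10 = 2.7, 27 × 0.20 = 5.4. That is about 1 to 5 patients. It is an upper bound for each assumed rate, because by step 2 some of these stops still leave a score.

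**4. What the loss costs in precision**

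Detectable difference in SD units = (1.96 + 0.84) × √(1/n + 1/(2n)), where n is the number of controls. This assumes two-sided alpha 0.05, 80% power and a normal approximation; none of these is in the protocol.

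- 18 vs 9: 2.80 × √(1/9 + 1/18) = 1.14 SD
- 16 vs 8 (three patients lost): 1.21 SD
- 14 vs 7 (six patients lost): 1.30 SD

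The loss of precision is moderate. The larger worry is which patients are lost.

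**5. Timing of the last session**

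Weeks from session 3 to the last session = (number of cycles − 3) × interval. Assuming 4 to 8 cycles at 2- or 3-week intervals (not in the protocol), the shortest case is (4 − 3) × 2 = 2 weeks and the longest (8 − 3) × 3 = 15 weeks. The protocol leaves this gap open; it does not say that it differs between patients.

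**The case against.** The strongest reply is that this affects a hypothetical few patients on two secondary endpoints. The primary endpoint and endpoint a use numbered sessions and are untouched. The session before chemotherapy ends is a legitimate milestone. Handling of missing values is commonly left to the statistical analysis plan, which is not at hand. The stopping rate, the cycle numbers and the link between stopping and outcome do not come from the protocol.

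Much of this stands. What does not is the appeal to the analysis plan: it can say how a missing score is treated, but it cannot supply a State score that nobody asked for.

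A reader might be tempted by three stronger readings, which the document does not support:

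- *Every early stopper lacks a final value.* Not so under the endpoint text, as step 2 of the working shows.
- *The other patients are measured at unequal times, which biases b.* Unequal timing is inferred from silence about cycle number and interval. If it exists, randomisation balances it on average. It then mainly adds noise and blurs what b measures, although chance imbalance is possible with 27 patients.
- *The missing values are known to be informative.* This is plausible, but nothing in the document shows it.

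It is also fair to say that the mismatch between endpoints and schedule is the firmer defect. The missing State mark at Last cycle concerns every patient. Adding that mark is necessary, but it would not help a patient who stops unannounced between Cycle 3 and her planned end.

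**Conclusion.** The concern holds in a limited form. The final time point of b and d is not defined as planned or actual, and the schedule provides no assessment between Cycle 3 and Last cycle. Unannounced stops at session 4 or later, before the planned end, therefore leave no pre-session State or nausea score for the actual last session, and this cannot be repaired afterwards.

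The size is unknown. Under an assumed 5-20% rate of unexpected stopping it is at most about 1 to 5 of 27 patients, which matters mainly because each control is about 11% of her arm. Selective loss is a reasonable suspicion and no more. The consequence is confined to two secondary endpoints, and the remedy is worth making because it is cheap and works only if adopted before the data are collected.

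**What to change.** 1. From Cycle 4 on, collect STAI State and the 0-10 nausea score before chemotherapy at each cycle, in both arms.
2. In endpoints b and d, define the last session as the last one actually received. Endpoint b then compares the arms at the end of the chemotherapy each patient received, not at a fixed time after the music programme; the text should say so.
3. Bring the schedule into line with the endpoints: add the State mark before chemotherapy at the last cycle, the nausea marks before Cycles 2 and 3, and the new marks from Cycle 4, and state that the last-cycle nausea rating precedes chemotherapy.
4. Do not adjust for the number of cycles actually received since the third music session. That number arises after randomisation, early stopping helps determine it, and it is undefined for controls, who have no music session. If timing is to be adjusted for, record the planned number of cycles at inclusion and use that.

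The cost is a schedule amendment and, per patient, a few more short self-completed forms with one 0-10 item, at visits that take place anyway. The downside is some added questionnaire burden.

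### Secondary endpoint b needs a STAI State score before the last chemotherapy session, but the assessment schedule collects none after Cycle 3

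*Protocol*

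**What the plan says.** Section D of the Protocol defines secondary endpoint b as the change in anxiety between the first and the last chemotherapy sessions, "measured using the STAI State score (before the first session and before the last session"). It therefore rests on two State scores per patient, one of them taken just before the final session.

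The primary endpoint in the same section gives the only explicit collection instruction for this form: "The STAI State score will be collected before and after chemotherapy administration during the first three chemotherapy sessions". It does not mention the last session.

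Section E sends the reader elsewhere for timing: "see the assessment schedule for the timing of questionnaire administration". In that schedule the STAI YA (State) row is marked before and at the end of Cycles 1, 2 and 3 and nowhere else. The STAI YB (Trait) row is marked before Cycle 1 and at M6. The last cycle has its own column after Cycle 3, in the follow-up block. Unlike Cycles 1 to 3, it is not divided into a before and an end assessment.

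**The concern.** The endpoint definition and the schedule disagree on whether a State score is taken at the last cycle. Section E defers to the schedule for timing, so staff will probably work from the table, and the table omits the assessment.

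What would be lost is specific. Music therapy is given only at the first three cycles. Endpoint a stops before the third session, when two of the three music sessions have been given. Endpoint b is the only listed endpoint that looks at State anxiety at a later chemotherapy visit, after the music sessions have ended, and so the only one that can show whether an effect on State anxiety lasts. A State score describes how the patient feels at that moment. If it is not taken before the last session, it cannot be reconstructed afterwards.

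**Working it through.** The protocol states no figure to reproduce here. The check counts the State scores the endpoints need and compares them with the crosses in the schedule.

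**Step 1. State scores required (section D)**

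| Endpoint | State time points | New time points |
|---|---|---|
| Primary | before and after chemotherapy, sessions 1, 2, 3 | 2 × 3 = 6 |
| Secondary a | before session 1, before session 3 | 0 (both already counted) |
| Secondary b | before session 1, before the last session | 1 (before the last session) |

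Total required: 6 + 0 + 1 = 7.

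**Step 2. Crosses in the Study Assessment Schedule**

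| Row | C1 before | C1 end | C2 before | C2 end | C3 before | C3 end | Last cycle | M6 |
|---|---|---|---|---|---|---|---|---|
| STAI YA (State) | X | X | X | X | X | X | – | – |
| STAI YB (Trait) | X | – | – | – | – | – | – | X |
| QLQ C30 | X | – | – | – | – | X | X | – |
| BR23 | X | – | – | – | – | X | X | – |
| Nausea scale | X | – | – | – | – | X | X | – |

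State scores scheduled: 6. Shortfall: 7 − 6 = 1, the score before the last session. Endpoint b needs two scores and the schedule supplies one.

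**Step 3. Is the blank cell a fault of the table as read?** This is unlikely. The six State crosses fit the six columns of Cycles 1 to 3 exactly and match the six assessments of the primary endpoint. Three other rows carry a cross under the last cycle, so that column is intact and in use.

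**Step 4. Can another assessment stand in?** No. The only STAI form after Cycle 3 is the Trait form at M6. Section E separates the two scales: "Trait Anxiety, which reflects the patient's general and habitual emotional state", whereas the State form reflects the current emotional state. The visit is also different.

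**Step 5. Size.** The design is "Randomized study (2:1 allocation ratio") with 27 subjects. With exact allocation that gives 27 × 2/3 = 18 in the music arm and 27 × 1/3 = 9 in the control arm. If the schedule is followed, evaluable pairs for endpoint b are 0 of 18 and 0 of 9, that is 0 of 27.

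**Step 6. Would one cross under the last cycle be enough?** Not by itself. The column has no before/end division, so a cross there could be met by a score taken after chemotherapy, which is not what endpoint b defines.

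**The case against.** The strongest reply is that the endpoint text is protocol text too. It names the instrument and the time point, so the document contradicts itself rather than designing the assessment out. A site working from section D could collect the score. On that view, zero evaluable pairs is the worst case under one reading. This is fair, and the figure should be given with its condition. It does not rescue the endpoint: collection that depends on which page staff consult would be unplanned and probably incomplete. With about 9 control patients, each missed score would remove about 1/9 = 11% of that arm.

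The number of cycles is not stated, so a patient's third cycle could in principle be her last. Her score before Cycle 3 would then serve, but for her endpoint b would equal endpoint a. The schedule treats the last cycle as a separate, later visit.

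Other anxiety measures are planned late in the trial: the PROMIS-29 anxiety domain under endpoint c, and STAI Trait at M6. Neither is a State score, and PROMIS-29 itself has no row in the schedule.

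Two further points stand. Only one secondary endpoint is affected; the primary endpoint and endpoint a have every score they need. The gap is also part of a wider mismatch: the schedule lists QLQ C30 and BR23, which no endpoint uses, and its nausea row does not match the time points of endpoint d. That argues for checking the whole table against the endpoints, and does not excuse this cell.

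**Conclusion.** The concern holds. The Protocol defines an endpoint on a score that its own schedule does not collect: seven State time points are needed and six are scheduled. Followed as written, the schedule leaves endpoint b with 0 of 27 evaluable pairs.

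That figure assumes that sites follow the schedule, as section E directs, and that the last cycle comes after the third. If some sites' staff follow the endpoint text instead, the result is irregular collection rather than total loss.

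The error should be corrected before patients reach their last cycle. It is an internal contradiction, not a detail that can be left to a statistical analysis plan, because an analysis plan cannot supply uncollected data. The conclusion involves no alpha, power or variance assumption.

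**What to change.** In the Study Assessment Schedule, split the last-cycle column into before chemotherapy and end of chemotherapy, as is done in substance for Cycles 1 to 3. Put a STAI YA cross under before chemotherapy, applying to both arms. Extend the collection sentence in section D so that it also names the State score before the last session. When the column is split, assign the crosses already there (QLQ C30, BR23, nausea) to the correct side, checking each against its endpoint.

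The cost is one short self-questionnaire per patient at a visit that already has patient-reported assessments, plus a protocol amendment and, if the case report form mirrors the schedule, a matching change there. The number of subjects does not change.

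If the sponsor does not want the extra assessment, the alternative is to remove or redefine endpoint b. That also resolves the contradiction, but it gives up the only test of whether an effect on State anxiety persists after the music sessions end.

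### The quality-of-life endpoint rests on PROMIS-29, but the assessment schedule collects QLQ-C30 and BR23 and has no PROMIS-29 row

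*Protocol*

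**What the plan says.** Three places in the Protocol bear on which quality-of-life form patients receive.

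- **Section D, Secondary objectives and endpoints, item c.** The endpoint is "Changes in quality of life, measured using the PROMIS-29 questionnaire at study inclusion", and then "at the end of the third chemotherapy session, and at the end of all chemotherapy sessions". This fixes one instrument and three times.
- **Section E, Description of Quality-of-Life Questionnaires.** Participants are to complete the questionnaires listed there, which are the STAI and PROMIS-29 and no others. The text describes the second in detail: "The PROMIS 29 Profile v2.0 assesses pain intensity using a single numeric rating item (0 to 10) and evaluates seven health domains". For timing it sends the reader elsewhere: "see the assessment schedule for the timing of questionnaire administration".
- **Study Assessment Schedule.** The patient-reported block has five rows: STAI trait, STAI state, QLQ-C30, BR23 and the 0–10 nausea scale. QLQ-C30 and BR23 carry three marks each. There is no row for PROMIS-29.

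**The concern.** The endpoint and the data collection name different instruments. The text that defines the endpoint and describes the questionnaires knows only PROMIS-29. The table that says what to hand out and when knows only QLQ-C30 and BR23.

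Changes in PROMIS-29 domains need PROMIS-29 answers, and the Protocol offers no mapping from the other two forms. Three outcomes are possible:

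- **The schedule is followed.** The pre-specified endpoint has no data.
- **The text is followed.** PROMIS-29 is collected, but outside the table that is meant to govern timing.
- **Both are collected, or the gap is noticed late.** The quality-of-life instrument can then be chosen after data are in hand. The trial is open-label, so that choice could be made with knowledge of the arms.

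A later analysis plan cannot repair this, because it can only analyse forms that were completed.

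**Working it through.** The Protocol states no figure to reproduce here, so the check is a side-by-side reading followed by a count.

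**Comparison of the three places**

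| Item | Endpoint c (section D) | Questionnaire description (section E) | Study Assessment Schedule |
|---|---|---|---|
| PROMIS-29 | Named as the instrument | Described, v2.0 | No row |
| QLQ-C30 | Not mentioned | Not mentioned | Row with 3 marks |
| BR23 | Not mentioned | Not mentioned | Row with 3 marks |
| First assessment | Study inclusion | Refers to schedule | Cycle 1, before music therapy; inclusion column empty |
| Second assessment | After session 3 | Refers to schedule | Cycle 3, end of chemotherapy |
| Third assessment | After all sessions | Refers to schedule | Last cycle |

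**Could the missing row be lost text?** This is unlikely. The patient-reported block runs without a gap from its heading to the intervention block. Two other named quality-of-life forms stand where PROMIS-29 would be expected, and nothing there is redacted.

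**Do the times agree?** Nearly. The QLQ-C30 and BR23 marks fall at about the three times of endpoint c, except that the first is before cycle 1 rather than at inclusion. This pattern suggests a change of instrument that was not carried through the whole document. It also shows a second, smaller mismatch in the baseline.

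**Count of forms.** The inputs are 27 patients (section A), three times (endpoint c) and two forms with three marks each (schedule). Full completion is assumed, so these are upper bounds.

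- PROMIS-29 forms implied by endpoint c: 27 × 3 = 81. Forms scheduled: 27 × 0 = 0.
- QLQ-C30 and BR23 forms scheduled: 27 × 3 × 2 = 162. Number of these tied to an endpoint: 0.
- Arm sizes under 2:1 allocation: 27 × 2/3 = 18 and 27 × 1/3 = 9. With 9 controls there is little room for some patients to be on one instrument and some on another.

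**The case against.** The contradiction itself is not in dispute. The case for giving it less weight has four parts.

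1. **The loss is not certain.** Section E tells participants to complete PROMIS-29 and uses the schedule only for timing, and endpoint c states its own times. A team working from the text would collect the right form. This stands, and the loss must be stated as conditional on following the schedule. The contradiction remains, because the schedule would still ask for two forms that have no purpose.
2. **The schedule may be the current version.** Two agreeing sections do not prove that the third is out of date. The schedule names specific instruments with coherent marks, and the Protocol does not say which version is current. This stands as a caution. Agreement between sections D and E supports restoring PROMIS-29 as the default, but the sponsor should confirm which forms are in use before deleting any rows.
3. **The form counts measure no bias or loss of precision.** This is true. They show only that the gap is complete rather than partial.
4. **It is one of four secondary endpoints.** This is also true, and the primary comparison is untouched. Even so, an entire pre-specified endpoint has no scheduled source of data, and a missed baseline form cannot be obtained later.

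**Conclusion.** The concern holds. The Protocol contradicts itself on the quality-of-life instrument, and as written the schedule supplies none of the data that endpoint c needs: 0 of 81 PROMIS-29 forms, with 162 forms of two other questionnaires collected for no stated objective. The figures assume that the schedule is followed and that all 27 patients complete every assessment.

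This is an internal inconsistency, not detail left to an analysis plan. It must be fixed because the loss could not be undone once patients have passed the assessment times. The damage is confined to secondary endpoint c; the conclusion on the primary STAI State comparison does not depend on it.

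**What to change.** First confirm which forms are in use. Then bring endpoint c, the questionnaire description and the schedule to one instrument set.

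- **Default.** Replace the QLQ-C30 and BR23 rows by one PROMIS-29 row at the three times in endpoint c. Sections D and E then stay as they are.
- **Alternative, if QLQ-C30 and BR23 are intended.** Rewrite endpoint c and the description in section E around them, and state which scores form the endpoint.
- **Baseline.** In either case, settle whether the first form is completed at inclusion or just before cycle 1, and use the same time in endpoint c and the schedule.
- **Timing.** Make the change before data collection. If collection has begun, make it before any comparison by arm, and document which forms patients actually received and why the instrument was chosen.

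The cost is a small amendment to the schedule, and to the case report form if it mirrors the schedule. Under the default, quality-of-life forms per patient fall from 2 × 3 = 6 to 1 × 3 = 3. The Protocol does not give the length of QLQ-C30 or BR23, so the change in the number of items cannot be stated from it.
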